1.0 Objectives

1.1 Study Objectives

Our long term goal is to understand the likely health effects of cigarette smokers switching to a Standardized Research E-Cig (SREC) and to assess the role of nicotine delivery on switching, acceptability and markers of health outcomes. The specific objective of this proposal is to recruit a cohort of 240 current exclusive daily cigarette smokers and to measure a comprehensive battery of health markers at baseline and at 3 and 6 weeks after attempting to switch completely to SRECs containing either zero or 58 mg/ml nicotine in a randomized double-blind, placebo-controlled design with the following three specific aims:

- **1.1.1** Aim 1: To characterize the short-term effects of attempting to switch from traditional cigarette smoking to a Standardized Research E-Cig from baseline to 6 weeks using a comprehensive battery of measures (e.g. carcinogen biomarker (NNAL), pulmonary function testing, Holter EKG, exhaled CO, and cotinine, BP etc.).
 - **1.1.1.1** Our hypothesis is that attempting to switch to a SREC will result in a reduction in markers of harms to health, as compared with the baseline (exclusive cigarette smoking) measures.
- **1.1.2** Aim 2: To compare the effects of switching to a standardized research electronic cigarette (SREC) with pods containing 58 mg/ml nicotine liquid versus 0 mg/ml nicotine liquid on smoking behavior and changes in health markers at 6 weeks post-switching.
 - **1.1.2.1** Our hypothesis is that nicotine-containing SRECs will facilitate switching from smoking more efficiently than zero nicotine SRECs and will result in a significantly greater improvement in markers of health risk, but will conversely result in higher ratings of dependence on the SREC (as compared to the zero nicotine SREC) at 6 weeks post-switching (after controlling for baseline measures).
 - **1.1.2.2** We also hypothesize that the nicotine-containing SRECs, (as compared with the zero nicotine SRECs, after controlling for baseline) will result in a lower total score for the withdrawal items on the MNWS and lower mean scores on ratings of cigarette craving, during the first week of the trial.
- **1.1.3** Aim 3: At the end of each participant's 6 week participation, they will be provided with information about the health effects of tobacco product use, how to purchase their own electronic cigarette and supplies if they wish to continue using one, and sources of assistance to quit smoking. They will then be asked to complete telephone and online survey four weeks later (10 weeks after switching).
 - 1.1.3.1 Our hypothesis is that participants randomized to nicotine-containing SRECs (as compared with those randomized to zero nicotine liquid) will be more likely to continue to try to abstain from cigarettes and to continue to use an e-cig at week 10 follow-up.

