1.2 Primary Study Endpoints

The primary endpoint for the study is creatinine-corrected urinary NNAL concentration at 6 weeks (after switching).

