1.3 Secondary Study Endpoints

Secondary outcomes for the study include changes in pulmonary function (FEV-1), tobacco-related toxicant concentrations, such as exhaled CO, EKG markers (HRV, PVCS, ST elevations, WRS duration),

urine cotinine, and blood pressure at 6 weeks, controlling for baseline measures. In addition, nicotine withdrawal and cravings, measured on the MNWS, at 1 week controlling for baseline. Finally, the average number of cigarettes smoked per day (CPD) and measures of dependence (e.g. FTND, PSECDI) will be analyzed. Outcomes at the 10 week telephone follow-up include the average number of cigarettes smoked per day in the week prior to the follow-up call, the number of days on which an e-cig was used in the previous 21 days, and the self-reported cigarette abstinence (zero cigarettes smoked in the prior week).

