8.3 Statistical methods

For the analysis, the baseline time will be Visit 1, prior to randomization to an e-cig nicotine content regimen (placebo or nicotine), which occurs at end of Visit 1.

Summary statistics will be provided for baseline smoking characteristics, along with other study demographics collected upon enrollment/screening at Visit 1. Summary statistics will also be provided for all variables at each visit. This will include all randomized subjects.

Aim 1: For each battery of measures, the mean change from week 1 to week 6 will be estimated with a corresponding 95% confidence interval. The p-value for testing zero underlying change will also be provided. This analysis will be conducted separately for the two treatment arms. To adjust for multiple comparisons, the false discovery approach will be used. Additionally, the trajectory of each measurement at visit 1 visit 2 and visit 3 will be modeled using linear mixed effects regression.

Aim 2: The difference between the two treatment arms on markers of health risk will be analyzed. The primary conceptual framework is a modified intent-to-treat: subjects will be analyzed by their randomized arm regardless of compliance with the e-cig nicotine content regimen, as long as data for the particular outcome is available at either of the post-randomization visits (Visit 2 or Visit 3). The basic statistical tool will be linear regression or logistic regression. Two sets of regressions will be conducted. The first set of regressions will model the dependence of the outcome measures at week 6 on the two treatment arms while controlling for the baseline value of the outcome variable. The second set of regressions will adjust for additional covariates at baseline (V1), to be selected via backward elimination at 0.05 significance level. These additional covariates will be chosen from the following list based on appropriateness for the specific outcome variable.

- Age
- Race
- Hispanic
- Education status
- Gender
- Income
- SDOH questionnaire (ACES score)
- Baseline cpd
- Baseline CO
- Baseline NNAL
- Baseline cotinine
- Menthol/non-menthol cigarettes
- Cigarette length
- Height
- Weight
- BMI

- Baseline FEV1
- Baseline PSCDI
- Quit attempt history
- "Currently, do you have any symptoms or a disease that you believe is caused or made worse by your tobacco use?" (yes/no)
- Perceived cessation support questions
- ETS questionnaire
- Baseline MNWS
- Baseline QSU
- Baseline audit c

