- Baseline cigarette perceived health rick score
- E-cig Perceived risk/Perceptions of e-cig risks (from screener)
- Baseline CESD
- Baseline Kessler 6
- Baseline perceived stress
- Baseline COPD questionnaire
- Baseline interheart
- Importance and confidence to quit

Same strategy will be used for withdrawal items on the MNWS and scores on ratings of cigarette craving. The analysis will be conducted for the values of these variables at week 3, however.

Cigarette Abstainers Subgroup Analysis

In addition to the intent-to-treat analysis, additional analysis on subgroup of regular cigarette abstainers only will be conducted. By design, this subgroup will only consist of Switching Phase Completers (still in the study at the time of V3) who have successfully abstained from cigarette and other tobacco use (except e-cigs) from 1 week prior to V2 consistently and consecutively until V3. Therefore, this subgroup would be defined as 'quit' for at least 4 weeks. Participants in this sub-group must also have an exhaled CO < 6 ppm at both V2 and V3. Based on our previous data, we believe that 40% of the nicotine e-cig group (84 x .40 = roughly 33 participants) and 20% of the placebo e-cig group (84 x .20 = roughly 16 participants) will be classified as abstainers. For this relatively small subgroup, we shall only model the dependence of the outcome measures at week 6 on the two treatment arms while controlling for the baseline value of the outcome variable. No elaborate adjustment of other covariates will be included.

Aim 3: The proportions of subjects who will try to abstain from cigarettes and who will continue to use an e-cig at week 10 will be compared between the two arms using Fisher's exact test. Switching Phase dropouts will be treated as 'non-abstainers' from cigarettes under the 'worst case-scenario' assumption. A supplementary logistic regression will also be conducted to explore their dependence on demographic variables in addition to the two treatment arms.

Multiple imputation for missing values

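### Aim 2 hypothesises that nicotine SRECs help smokers switch by week 6, but the plan defines no week-6 switching endpoint and compares none between arms

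*Combined protocol and SAP*

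**What the plan says.** Section 1.1.2 sets Aim 2 as a comparison of the two nicotine contents "on smoking behavior and changes in health markers at 6 weeks post-switching". Its first hypothesis, in 1.1.2.1, opens with the claim that "nicotine-containing SRECs will facilitate switching from smoking more efficiently than zero nicotine SRECs".

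The endpoints are these:

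- Section 1.2: "The primary endpoint for the study is creatinine-corrected urinary NNAL concentration at 6 weeks".
- Section 1.3, week 6: a list of health and exposure measures that includes exhaled CO and urine cotinine, adjusted for baseline.
- Section 1.3, no time point: "the average number of cigarettes smoked per day (CPD) and measures of dependence".
- Section 1.3, week-10 telephone call: "self-reported cigarette abstinence (zero cigarettes smoked in the prior week", among other items.

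In section 8.3 the Aim 2 paragraph begins: "The difference between the two treatment arms on markers of health risk will be analyzed". It plans linear or logistic regressions of week-6 outcomes on arm, adjusted for baseline, and names no switching or abstinence outcome.

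The abstainer subgroup analysis in 8.3 does define verified abstinence. Members must still be in the study at V3 and must have abstained from cigarettes and other tobacco (e-cigs excepted) from one week before V2 through to V3. In addition: "Participants in this sub-group must also have an exhaled CO < 6 ppm at both V2 and V3". The plan expects 40% of 84 in the nicotine arm and 20% of 84 in the placebo arm to qualify. It then compares other outcomes by arm within that group.

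Section 7.2.8 holds a second definition, for selecting interviewees: no cigarettes in the past 7 days at both Visit 3 and Phone Contact #5, with CO below 6 ppm at Visit 3 only.

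Fisher's exact test on abstinence and e-cig use appears only under Aim 3, at week 10, where people who leave during the switching phase count as not abstinent.

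**The concern.** The hypothesis is about switching, and the inclusion criteria require willingness to stop cigarettes completely. Yet the plan treats complete switching as a condition for entering an analysis, not as an outcome. Comparing markers among abstainers selects on something that happens after randomisation and that treatment is expected to affect. Such a comparison is not protected by randomisation and cannot show whether nicotine increased switching. The comparison that can, the proportion switched among everyone randomised, is not planned.

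There is also a pre-specification problem. With two CO-verified definitions in the document and neither named as an endpoint, any later statement about switching at week 6 could rest on a definition chosen after the data are seen.

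**Working it through.** **1. Matching the hypothesis to the analyses.** To test the switching clause, an analysis must concern complete switching, fall at week 6, and compare the arms as randomised.

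| Item | Complete switching? | Week 6? | Compared by randomised arm? |
|---|---|---|---|
| NNAL (1.2) | No | Yes | Yes |
| Exhaled CO (1.3) | No, continuous level | Yes | Can be read into 8.3 |
| Cigarettes per day (1.3) | No, average count | Not stated | Can be read into 8.3 |
| Abstinence at the phone call (1.3, Aim 3) | Yes, self-report | No, week 10 | Yes |
| Abstainer subgroup (8.3) | Yes, CO-verified | Through V3 | No, used as a condition |
| Interview definition (7.2.8) | Yes, CO at V3 | V3 and week 10 | No, used for selection |

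No row meets all three requirements.

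**2. The plan's own power figure.** Section 8.2 gives 120 × 0.70 = 84 per arm, a difference of 35, an SD of 69 and 5% type 1 error (taken as two-sided).

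Power = Φ(35 / (69 × √(2/84)) − 1.96) = Φ(35/10.65 − 1.96) = Φ(1.33) = 90.8%.

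This agrees with the stated figure of at least 90%. The documents give no power for switching.

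**3. Power of the missing comparison, from the plan's expected rates.**

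Expected abstainers: 84 × 0.40 = 33.6 and 84 × 0.20 = 16.8. As shares of all randomised, with dropouts counted as not switched: 33.6/120 = 28% and 16.8/120 = 14%.

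Normal approximation: power = Φ((d − 1.96 × SE₀)/SE₁), where d = p₁ − p₂, SE₀ = √(2p̄(1 − p̄)/n) and SE₁ = √((p₁(1 − p₁) + p₂(1 − p₂))/n).

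- 84 completers per arm, 40% vs 20%: SE₀ = √(0.42/84) = 0.0707 and SE₁ = √(0.40/84) = 0.0690. Power = Φ((0.20 − 0.1386)/0.0690) = Φ(0.89) = 81%.
- 120 randomised per arm, 28% vs 14%: SE₀ = √(0.3318/120) = 0.0526 and SE₁ = √(0.322/120) = 0.0518. Power = Φ((0.14 − 0.1031)/0.0518) = Φ(0.71) = 76%.

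Exact power of the two-sided Fisher test is the summed binomial probability of all tables with p < 0.05:

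| Setting | Normal approximation | Fisher exact |
|---|---|---|
| 40% vs 20%, 84 per arm | 81.3% | 77.1% |
| 28% vs 14%, 120 per arm | 76.2% | 71.6% |
| 40% vs 20%, 120 per arm | 92.7% | 90.8% |

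The last row applies only if the expected rates held among all randomised participants. The plan's own multiplication by 84 does not imply that.

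**The case against.** The strongest reply is that smoking behaviour is already covered. Exhaled CO is a listed week-6 outcome, and section 7.4.4 says CO is collected to check smoking intensity. Cigarettes per day is a listed outcome, recorded by diary up to Visit 3 (7.2.10). The week-6 regressions in 8.3 refer to outcome measures generally and allow logistic models. Aim 2 does not itself say that switching means verified abstinence.

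Much of this stands. A reader might infer that the trial makes no week-6 comparison of smoking at all, and the documents do not support that. But a halved average arises equally if half an arm stops or if everyone halves, so neither measure isolates complete switching. Nor does the mention of logistic regression supply the missing test. No binary outcome is named, and the models adjust for the outcome's baseline value, which for abstinence is the same for everyone because all entrants must be smoking.

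Three other stronger readings also fail:

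- That verified abstinence serves only to form the subgroup. Section 7.2.8 also uses a CO-verified definition, for interview selection.
- That week 10 falls after participants have no product left. Some unused pods may be kept at Visit 3 (7.2.6.2.4), and disposal follows Phone Contact #5 (7.4.6.4).
- That the number switched would go unreported. The subgroup analysis needs the count in each arm, so it would normally appear. What is missing is a pre-specified endpoint and test.

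**Conclusion.** The point holds in this form: Aim 2 states a week-6 switching hypothesis, but the plan has no defined week-6 switching endpoint and no planned between-arm comparison of one. Two CO-verified definitions exist and neither is compared by arm. The week-10 abstinence comparison serves a different aim, is self-reported, and comes four weeks after the switching phase.

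The size is limited. NNAL remains the primary endpoint, and neither its analysis nor its power is affected. The added comparison would have about 72% exact power in all randomised participants and 77% among completers, so it is informative but not powered at 80%. These figures describe the proposed test and do not measure harm from its absence. They rest on three assumptions: two-sided 5% error, the plan's 40% and 20% applying to completers, and 30% dropout in each arm.

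**What to change.** In sections 1.3 and 8.3, add one secondary endpoint: sustained CO-verified abstinence from one week before V2 through V3, with CO below 6 ppm at V2 and V3, exactly as the abstainer subgroup is already defined. Describe it as sustained abstinence, nominally day 14 to day 42, and not as status at week 6. State that it differs from the interview definition in 7.2.8.

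Compare it between arms in all 240 randomised participants, counting dropouts as not switched. Use Fisher's exact test with the supplementary logistic regression, as already planned for Aim 3. In 1.3, give week 6 as the time point for cigarettes per day.

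The cost is a few sentences and one more secondary test. The diaries and CO readings are already scheduled, so no new visits, assays or participants are needed. The drawback is that anyone who switches fully only after V2, or who lacks a V2 CO reading, counts as not switched. The text should say so.

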1.2 Primary Study Endpoints

The primary endpoint for the study is creatinine-corrected urinary NNAL concentration at 6 weeks (after switching).

1.3 Secondary Study Endpoints

Secondary outcomes for the study include changes in pulmonary function (FEV-1), tobacco-related toxicant concentrations, such as exhaled CO, EKG markers (HRV, PVCS, ST elevations, WRS duration),

urine cotinine, and blood pressure at 6 weeks, controlling for baseline measures. In addition, nicotine withdrawal and cravings, measured on the MNWS, at 1 week controlling for baseline. Finally, the average number of cigarettes smoked per day (CPD) and measures of dependence (e.g. FTND, PSECDI) will be analyzed. Outcomes at the 10 week telephone follow-up include the average number of cigarettes smoked per day in the week prior to the follow-up call, the number of days on which an e-cig was used in the previous 21 days, and the self-reported cigarette abstinence (zero cigarettes smoked in the prior week).

2.0 Background

2.1 Scientific Background and Gaps

Tobacco smoking is the leading preventable cause of premature morbidity and mortality in the U.S.¹ and cessation provides immediate and sustained improvement in health.² Cigarette smoking harms almost every organ in the body, but the lungs and the cardiovascular system are particularly affected. Thus, cigarette smokers aged 35-64 have a greater than 3-fold risk of death from ischemic heart disease and cerebrovascular diseases and more than a 10-fold risk of death from chronic airway obstruction or lung cancer, compared with never cigarette smokers.¹ These effects and the mechanisms causing them are relatively well understood. Similarly, there is clear evidence that the risks of suffering from and eventually being killed by these smoking- caused diseases reduce significantly if a smoker quits smoking completely. Thus, the clear message for smokers is that the single best thing they can do for their health is to quit smoking completely.

Over the past ten years, a new inhaled nicotine device, commonly referred to as an electronic cigarette (e-cig), has become increasingly popular around the world, particularly in the United States where more than 79% of US adults are currently aware of the devices and 3.7% are using one on a regular basis.³ Current e-cig use is most prevalent among current smokers (15.9%) and recent ex-smokers (22.0%) and is very uncommon among adult never cigarette smokers (0.4%).³⁻⁵ As the popularity of these devices has increased, the types of devices and the associated products available to users have diversified, making it difficult for users and non-users alike to understand the devices and their potential harms or benefits.

Though e-cigs are generally considered to be safer than traditional combustible cigarettes, the devices do deliver fine particles when the solvents (propylene glycol, vegetable glycerin, flavors, additives, and nicotine) are aerosolized and adequate assessments of cardiovascular and pulmonary health outcomes related to e-cig use are lacking.⁶ Recently, the National Institute on Drug Abuse (NIDA) developed a Standardized Research E-Cig (SREC) which is available in both medium (58 mg/ml) and placebo (zero mg/ml) nicotine liquid concentrations. The availability of this new device offers researchers the possibility of testing the likely health effects on users who are attempting to switch from cigarette smoking to e-cigs.

2.2 Previous Data

One study found that after 5 minutes of ad lib e-cigarette use, healthy adult cigarette smokers showed an increase in airway resistance, but no effect on other spirometry parameters such as forced vital capacity (FVC), forced expiratory volume in 1 second FEV1), and ratios of these values (FEV1/FVC).⁷ Other studies have examined changes in lung and cardiovascular function over a longer time in smokers attempting to quit smoking by switching to e-cigs. For example, Cibella et al⁸ found that smokers who completely switched to e-cigs and quit smoking showed steady improvement in their FEV (25-75%) and improvement in respiratory symptoms, including the time period when many continued using their e-cigs. This is consistent with the idea that smoking has a more severe adverse effect on lung function than e-cig use. Laboratory studies have also examined some acute cardiovascular effects of e-cig use and compared these with acute cigarette smoking. Farsalinos et al⁹ examined the immediate effects of electronic cigarette use on left ventricular (LV) function, compared to the well-documented acute

adverse effects of smoking. They found that although acute smoking caused a delay in myocardial relaxation, electronic cigarette use had no such immediate effects. Farsalinos et al¹⁰ also examined the effects on heart rate and blood pressure of switching from cigarettes to e-cigs in a smoking cessation trial, and reported that smokers who reduce or quit smoking by switching to e-cigarettes may lower their systolic BP in the long term. While these and other studies confirm the known cardiopulmonary effects of acute smoke and other nicotine aerosol inhalation, they provide only limited information about the cardiopulmonary effects of e-cig use because they typically study the effects of only one type of e-cig (usually a first generation or "cigalike" model), and focus more on the effects of change in smoking behavior rather than carefully assessing the effects of e-cig use per se. These studies have also included relatively basic cardiovascular outcomes (e.g., blood pressure and heart rate). These acute laboratory studies also typically selected a single device to study and were unable to examine the effects of chronic use of these products. One study has examined some effects in existing cohorts of (a) e-cig users who had quit smoking an average of 8 months earlier (b) cigarette smokers and (c) dual users over 24 months.¹¹ This study found that exclusive e-cig users were most likely to remain tobacco abstinent (61%), but that dual users were more likely to return to exclusive smoking than to guit smoking. There were few serious adverse events and detailed cardiopulmonary measures were not systematically recorded. The only significant finding on health outcomes was that dual users experienced improvements in self-rated health compared with those who continued smoking. An earlier one year follow-up on these cohorts found that the exclusive e-cig users reported a small but significant improvement in self-reported health as compared with the smokers.¹²

2.3 Study Rationale

Study of the health effects of e-cigs is in its infancy, and there are very few randomized placebocontrolled studies on the effects of switching to a well-characterized standardized e-cigarette on subclinical markers of cardiopulmonary and health risks. We propose to conduct what would be the first such study in the United States.

